Estimates from the literature were used to calculate the sample size needed for this study for the outcomes of changes from month 0 to month 5 in our primary outcome, heart failure quality-of-life. We assumed that the standard deviations (SD) seen in the current study would be similar to that in a similar study conducted in an urban setting in the United States.¹³ Sample size calculation were based assuming 80% power for a two-sided test at alpha of 0.05, and SD of 20.0. With the outcome of change in heart failure quality of life score from baseline to 5 months, considering as a minimum clinical difference of 10 points in the heart failure quality of life score, the sample size

needed was 63 individuals in each arm. We assumed a retention in the current study of 80%, thus the sample size needed at recruitment was at least 158 (n=79 in each arm)

8) Framework

The superiority hypothesis testing framework will be used, testing whether exposure to the intervention results in better outcomes than exposure to the control standard of care. Comparisons will be presented as differences between arms in changes in outcomes from baseline to 1 month to capture changes in acute heart failure symptoms and 30-day readmission; and from baseline to 5 months of follow-up to capture longer term and potentially sustained benefits.

9) Statistical interim analyses and stopping guidance

- a. Information in interim analyses specifying what interim analyses will be carried out and listing time points
 - i. None planned
- b. Any planned adjustment of the significance level due to interim analysis
 - i. No
- c. Details of guidelines for stopping the trial early
 - i. None

10) Timing of final analyses

Final analyses will begin in Fall 2021 upon completion of all field data collection in Fall 2020 and completion of all medical record data collection (Summer 2021).

11) Timing of outcome assessments

Research staff administered full surveys to both arms at baseline, 1 month, and 5 months. Additional brief surveys were collected at months 2 and 3. Medical record data were collected continuously in both arms from 3 months prior to baseline until 9 months after baseline.

Section 4: Statistical Principles

12) Level of statistical significance

95% confidence intervals and exact p-values (or $p<0.001$) will be reported.

13) Description and rationale for any adjustment for multiplicity and, if so, detailing how the type I error is to be controlled.

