 1. 16 (15.1%) of randomized intervention and 2 (2.3%) of randomized control participants were unable to be contacted by phone after the baseline evaluations.
 2. 6 (5.7%) participants allocated to the intervention and 2 (2.3%) participants allocated to the control arm were excluded because did not meet eligibility criteria after randomization, and 3 (2.8%) participants in the intervention arm were immediately re-hospitalized.
 3. 1 (0.9%) participant in the intervention arm died after being randomized.
 - ii. Lost to follow up (LTFU) occurred through loss of contact with study participants, moving out of the study area, and death. Intervention participants were also considered LTFU if they withdrew consent. Among

those that were randomized and contacted immediately after randomization (n=79 in intervention arm, and n=82 in control arm):

1. At month 1, 75 (94.9%) of intervention participants and 78 (95.1%) of control participants were retained from month 0.
2. At 5 months of follow-up, 60 (75.9%) of intervention participants and 59 (71.9%) of control participants were retained from month 0.

b. Timing of withdrawal/LTFU data

- i. Intervention participants left the study prior to their first encounter with Project Open Hand were considered withdrawn, otherwise they were considered LTFU.
- ii. Control participants that left the study prior the first call from UCSF staff were considered withdrawn, otherwise they were considered LTFU.
- iii. Participants that were excluded immediately after randomization were also considered early withdrawals.

c. Reasons and details of how withdrawal/LTFU data will be presented

- i. Withdrawal and LTFU data are presented in the CONSORT diagram, stratified by study arm and visit. These data are included to establish lack of bias in screening and retention between the two arms. (See appendix 2)

21) Baseline patient characteristics

We will evaluate several socio-demographic and clinical characteristics at baseline by which we will describe our study sample. These are outlined in Table 1 below and a shell table is provided in the appendix. We will stratify these characteristics by intervention and control arms and report median and the inter-quartile range for continuous variables with skewed data and mean and SD for continuous variables with normal distribution. Categorical variables will be presented as numbers and percentages. No significance testing will be conducted or reported at baseline per CONSORT guidelines.

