- i. Hospitalization and Emergency Department use: As a secondary Aim 1 outcome, self-reported data as well as abstracted medical record data on hospital readmission and Emergency Department use were collected. From the data we will assess the number of times participants were admitted to the hospital from baseline to 1 month and from baseline to five months and the cumulative probability of being hospitalized by study arm. The following outcomes will be reported:

1. Admissions to Zuckerberg San Francisco General Hospital from baseline to 1 month, as determined by medical records. Number of admissions to Zuckerberg San Francisco General Hospital from baseline to 1 month, by study arm, adjusting for baseline values (-3 to 0 months).
2. Admissions to Zuckerberg San Francisco General Hospital from baseline to 5 months, as determined by medical records. Number of admissions to Zuckerberg San Francisco General Hospital from baseline to 5 months, by study arm, adjusting for baseline values (-3 to 0 months).
3. Admissions to any hospital from baseline to 1 month, as determined by ZSFGH medical records and self-report of admission to hospitals other than ZSFGH. Number of admissions to any hospital from baseline to 1 month, by study arm, adjusting for baseline values (-3 to 0 months).
4. Admissions to any hospital from baseline to 5 month, as determined by ZSFGH medical records and self-report of admission to hospitals other

than ZSFGH. Number of admissions to any hospital from baseline to 5 months, by study arm, adjusting for baseline values (-3 to 0 months).

- a. Cumulative probability to be admitted to any hospital from baseline to 5 months by study arm.
- 5. Emergency room utilization at Zuckerberg San Francisco General Hospital from baseline to 1 month, as determined by medical records. Number of admissions to the emergency room at Zuckerberg San Francisco General Hospital from baseline to 1 month, by study arm, adjusting for baseline values (-3 to 0 months).
- 6. Emergency room utilization at Zuckerberg San Francisco General Hospital from baseline to 5 months, as determined by medical records. Number of admissions to the emergency room at Zuckerberg San Francisco General Hospital from baseline to 5 months, by study arm, adjusting for baseline values (-3 to 0 months).

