- a. **Preliminary/Descriptive analyses.** Frequency tables for all variables and measures of central tendency and variability for continuous variables will characterize the sample and be stratified by randomization arm to check for non-equivalence. If the two arms differ at baseline on any covariates, propensity scores approach will be used to obtain the desired marginal effect estimates under the counterfactual assumption of balanced arm.

25) Analysis methods to be used and how the treatment effects will be presented:

- a. Aim 1, Hypothesis 1. The intervention will lead to improved heart failure quality-of-life (primary outcome) and reduced acute care utilization (secondary outcomes) in the intervention arm compared to the control arm. Intent-to-treat analyses will assess whether the intervention will result in improved changes in primary and secondary outcomes with mixed effects models. These mixed models are equivalent to repeated measures models. Study arm (intervention or control), visits (baseline, month 1 and month 5), and the interactions between arms and visits will be the fixed effects and individuals will be considered as random effects.

Alternative analyses will be done using analysis of covariance in which the 5 month (and 1 month) outcome measures will be regressed on the corresponding baseline outcome measures and study arm. Analysis of covariance allows relaxing the assumption that the

baseline and follow-up measures have a 1:1 relationship and testing the assumption that the relationship between the baseline and follow-up measures are the same.

Additional analyses will be done to check robustness if the two arms differ at baseline by controlling for the propensity score or the covariates that were important in the propensity score.

For primary and secondary outcomes, Box-Cox transformations will be used to correct for skewness if needed.

To compare the probabilities of hospitalization and emergency room visits by study arm, a log-rank test will be performed, and visualized using Kaplan-Meier curves.

- b. Aim 2, Hypothesis, The intervention will improve food security, reduce healthcare utilization, and improve dietary behavior, that in turn will improve mental health (depressive symptoms), and medication adherence. Analysis for intermediate outcomes will be performed using mixed effects models, as described in Aim 1.
- c. Any planned sensitivity analyses for each outcome, where applicable: Not applicable.

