Any planned subgroup analyses for each outcome including how subgroups are defined: Additional models and statistical interactions (i.e., product terms) will be performed to identify characteristics of individuals who most benefitted from the intervention, such as biological sex, and food insecurity.

24) Missing data

- a. The study team employed several strategies to account for and address missing data during the CaRDS trial period. To prevent or reduce missing data, data collection was computerized, and the questions were obtained through a trained interviewer. The analyst will examine patterns of non-response and inspect distributions of mediating and outcome variables to identify outlying or unusual values and assess distributional characteristics. Missing data will be categorized into: 1) missed individual questions, 2) missing forms, and 3) missed visits.
- b. Missed individual questions: Multiple imputation will be used to address incomplete data arising from missing forms. The assumption will be that incomplete data arise from a conditionally missing-at random mechanism (MAR). Auxiliary variables will be included to help meet the MAR assumption and sensitivity analyses will be conducted with weighted multiple imputation to assess the MAR assumption. Information on percent of questions missing and imputed will be reported for each variable as appropriate in study manuscripts. Missing items from a scale will be imputing using the other items in the scale.
- c. Missed visits: When a participant missed a visit, either home or clinic or both, this was noted in the study register.

25) Additional analyses – None

26) Harms

i. Data safety:

The study team took several proactive strategies to insure the highest levels of data safety. First, data were collected on password protected tablets or laptops. Data were collected using REDCap and stored on a secure UCSF server. The data was stored in a separate folder than other study materials, and only members of the data team had access to this data. Lastly, any individual who requests study data was required to sign a data agreement which included not sharing the data as well as recommendations for data safety. No identifiers have or will be shared with external investigators.

ii. Details on how adverse events are coded or categorized:

Deaths were reported to UCSF by email within 24 hours after the PIs learned of the occurrence. Other adverse events were not reported.

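### The promised cumulative probability of admission has only Kaplan-Meier behind it and no rule for deaths; if deaths are censored, it is overstated slightly

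*Combined protocol and SAP*

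**What the plan says.** Section 6, item 22b.i.4a lists this Aim 1 secondary outcome: "Cumulative probability to be admitted to any hospital from baseline to 5 months by study arm". Under item 22b.i.4, any-hospital admissions come from the study hospital's records plus self-report for other hospitals.

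Item 25a gives the only method for the probabilities of hospitalization and emergency visits: "a log-rank test will be performed, and visualized using Kaplan-Meier curves".

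Death appears in Section 5, item 20a.ii: "Lost to follow up (LTFU) occurred through loss of contact with study participants, moving out of the study area, and death". Item 20a.i separately reports that "1 (0.9%) participant in the intervention arm died after being randomized", and this death is counted among the early withdrawals. By month 5, "60 (75.9%) of intervention participants and 59 (71.9%) of control participants were retained from month 0".

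On data capture, item 11 states: "Medical record data were collected continuously in both arms from 3 months prior to baseline until 9 months after baseline". Item 26.ii states: "Deaths were reported to UCSF by email within 24 hours after the PIs learned of the occurrence".

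The documents do not say when a participant is censored in these curves. They mention no competing event, cumulative incidence function or composite with death. Item 25c treats sensitivity analyses as not applicable, and the later item on additional analyses plans none.

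**The concern.** The outcome is a probability: the share of participants admitted by 5 months. Someone who dies without having been admitted can no longer be admitted. Censoring that person tells Kaplan-Meier to assume the same future admission risk as for those still alive. One minus Kaplan-Meier then estimates the admission probability in a setting where nobody dies first. It is never below the actual cumulative incidence, and it is strictly above it once any admission follows the death of someone not yet admitted.

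Participants enter while hospitalized for decompensated heart failure, so some deaths before readmission are plausible. At stake is the accuracy of a reported secondary result that readers will take as the observed risk of admission. The log-rank test is not at stake: with deaths censored it validly compares the admission rate among those alive and not yet admitted.

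**Working it through.** **The plan's own figures.** The only design calculation is for the KCCQ score: 2 × (1.96 + 0.842)² × (20/10)² = 62.8, so 63 per arm; 63/0.80 = 78.75, so 79 per arm and 158 in total. It reproduces, but has no bearing here. No event rate or power is given for the admission curves.

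**Inputs from the documents.** After early withdrawals, 79 intervention and 82 control participants remained. By month 5, 79 − 60 = 19 and 82 − 59 = 23 were not retained. The text does not say how many of these had died.

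**Inputs assumed.** The admission and death rates below are assumptions. Only deaths before a first admission matter.

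**Check 1: constant hazards over 5 months.** Let S be the value of one minus Kaplan-Meier and D the risk of death if admission did not intervene. Then a = −ln(1 − S), d = −ln(1 − D), and

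CIF = a/(a + d) × [1 − exp(−(a + d))].

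For S = 40% and D = 5%: a = 0.511, d = 0.051, and CIF = 0.909 × (1 − 0.60 × 0.95) = 0.909 × 0.43 = 39.1%.

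| One minus KM | CIF, D = 5% | Excess (points) | CIF, D = 10% | Excess (points) |
|---|---|---|---|---|
| 30% | 29.3% | 0.7 | 28.6% | 1.4 |
| 40% | 39.1% | 0.9 | 38.1% | 1.9 |
| 50% | 48.9% | 1.1 | 47.7% | 2.3 |

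**Check 2: fixing the share who actually die before admission.** Solve d/(a + d) × [1 − exp(−(a + d))] = p for d, with S = 40%.
- p = 1%: CIF 39.77%, excess 0.2 points.
- p = 2%: CIF 39.53%, excess 0.5 points.
- p = 5%: CIF 38.82%, excess 1.2 points.
- p = 10%: CIF 37.62%, excess 2.4 points.

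The most extreme combination tried (S = 60%, p = 10%) gives 4.0 points.

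**Check 3: counts.** Take 79 participants, 32 admitted (40.5%), evenly spaced events and no other censoring. With 1, 2, 4 and 8 deaths before admission, one minus Kaplan-Meier is 40.8%, 41.1%, 41.8% and 43.15%.

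**Sampling error for comparison.** At 40% with about 80 per arm, SE = √(0.40 × 0.60/80) = 5.5 points. The 95% interval is about ±11 points for one arm and 1.96 × √2 × 5.5 ≈ ±15 points for the difference.

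**Effect on the arm contrast.** Give both arms the same admission hazard (S = 40%), with D = 5% in one and 10% in the other. Kaplan-Meier shows 40% in both. Cumulative incidence shows 39.1% and 38.1%, about 1 point lower in the arm with more deaths.

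**The case against.** **The censoring rule is inferred.** The loss-to-follow-up definition describes study retention, while admissions come largely from continuously collected records. A retention category does not by itself fix a censoring time. If people who died were kept in the risk set to month 5 as not admitted, this bias would disappear. That stands: a reader might infer that the SAP says deaths are censored, and it does not. But it does not state the alternative either. Plain Kaplan-Meier together with death classed as loss to follow-up points to censoring, and the promised probability still needs a stated method.

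**The effect is small.** This also stands. Item 18 excludes anticipated life expectancy under a year, the horizon is 5 months, the trial is a pilot, and the outcome is one sub-item of a secondary outcome.

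**Distortion between arms.** A reader might infer that the planned curves would create a false difference between arms when mortality differs. The calculation does not support this: with equal admission hazards, Kaplan-Meier shows none. The 1-point gap arises in the cumulative incidence, so that curve should not stand alone.

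**Deaths may be visible elsewhere.** A reader might infer that nothing would reveal unequal mortality. Items 20 and 20c promise reasons for loss to follow-up by arm and visit in the CONSORT diagram, which could not be read here. Death counts may therefore be given there.

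**The analysis set.** Item 16a requires at least one follow-up visit, so someone who dies before any visit may be left out. That is a population question, and competing-risk estimation does not solve it.

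**Conclusion.** The concern holds as a minor one. The plan promises a cumulative probability, names a method that does not estimate it when deaths are censored, and leaves the handling of death unstated. On the natural reading the reported probability is too high. The size rests wholly on assumed rates: about 0.7-2.3 points for 30-50% by Kaplan-Meier with a 5-10% risk of death, and about 0.2-0.5 points at 40% if 1-2% die first. Even the extreme combination of 4.0 points lies well within the ±11-point interval for one arm. The log-rank test remains valid as a cause-specific comparison, and the KCCQ primary analysis is untouched. The documents do not support a claim that the planned analysis biases the comparison between arms.

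**What to change.** In item 25a:

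1. State how death and other losses are handled in the time-to-event analyses.
2. Estimate the cumulative incidence of first admission and of first emergency visit by arm with death as a competing event (Aalen-Johansen estimator).
3. Keep the log-rank test, labelled as the comparison of cause-specific rates.
4. Report deaths by arm next to these curves, separately from other losses to follow-up, and add time to death or first admission as a supporting comparison. This is needed because higher mortality can itself lower an arm's cumulative incidence of admission.

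The cost is a few sentences in the SAP and no new visits. The one practical task is to confirm dates of death from the death reports and medical records: item 26.ii says deaths were reported once the investigators learned of them, but not that dates were recorded or that deaths among participants lost to contact were sought.

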Appendix 1: Description of the intervention components

i. Medically tailored meals and groceries:

The five-month intervention followed a tapered model: participants received 100% daily nutrition during the first and second months following discharge from the hospital, 66% daily nutrition during the third month, and 33% daily nutrition during the fourth and fifth months. The intervention was designed to provide easy-to-prepare food during the first 30 days post-discharge and to gradually incorporate items requiring more preparation over the course of the study period. All food was delivered directly to participants' homes, unless they requested pick-up instead. The tapered medically-tailored meal (MTM) plan is summarized in Figure A1.1 and described below:

- a. **Month 1** (30 days, twice weekly deliveries): participants received two frozen medically tailored meals per day and supplies for daily breakfasts, including items such as milk, oats, cereal, yogurt, and fruit.
- b. **Month 2** (30 days, twice weekly deliveries): participants received one frozen medically tailored meal per day; supplies for daily breakfasts, as described above; and groceries equivalent to one meal per day. Each grocery bag contained 2 protein choices, $\frac{1}{2}$ dozen eggs, 2 dairy choices, 6 raw produce options, 2 bean options, and 3 grain options.
- c. **Month 3** (30 days, one weekly delivery): participants received one frozen medically tailored meal per day and groceries equivalent to one meal per day, as described above.
- d. **Month 4** (30 days, one weekly delivery): participants made the choice to receive either one frozen medically-tailored meal per day **or** groceries equivalent to one meal per day, as described above.
- e. **Month 5** (30 days, one weekly delivery): participants received groceries equivalent to one meal per day, as described above.

Figure A1.1 - Visual Overview of Tapered MTM Intervention

Month 1	Month 2	Month 3	Month 4	Month 5
 Daily breakfast   supplies 14 frozen meals/wk	 Daily breakfast  supplies  (7 meals/wk)	 Groceries  (7 meals/wk)	 Groceries (7 meals/wk)  OR 7 frozen meals/wk	 Groceries (7 meals/wk)

	7 frozen meals/wk			
--	-------------------	--	--	--

ii. *Nutrition education*: Participants in the intervention arm received monthly nutrition education and counseling with a Registered Dietician (RD). These sessions occurred at a location of participants' choosing (presumably home) for the initial and fifth encounters and over the phone for sessions during the second, third, and fourth months of the study period. During their assessments, RDs collected the following information: three-day food log, weight as reported by participant, quality of life questions, heart failure symptom control questions, and utilization of food resources. The five-month curriculum for RD visits is summarized below in Table A1.1.

Table A1.1 - Overview of RD Nutrition Education Visits

	Visit #1	Visit #2	Visit #3	Visit #4	Visit #5
Time point:	Within 14 days post-discharge from hospital	Between 30-60 days postdischarge	Between 60-90 days postdischarge	Between 90-120 days postdischarge	Between 120-150 days postdischarge
Location:	Participant's Home (or phone if preferred/ during COVID-19)	Phone	Phone	Phone	Participant's Home (or phone if preferred/ during COVID-19)
Visit Goals:	Instruct on how to keep a food log Review food plan for phases 1, 2, and 3 Select preferences for delivered grocery shop Review nutrition for heart failure	Check homework: review food log DASH Diet Meal pattern Instruct on fluid restriction + teach volume concepts Food Referral Chart	Follow up on food referral access- did they connect? Low Sodium diet and label reading	Navigate Eat Fresh (if internet access) or page 60, 61, 62 Recipe reading and use Provide written instruction for cooking and recipes	Shopping Skills Meal planning Cooking skills

Materials/ Recipes Covered:	Introduce education materials to be used over next visits: - Tenderloin Cooking School Book - Folder with handouts	Kitchen Basics- page 10	Spice Not Salt- page 34 Souped-up soup- page 13 ToasterRoasted Vegetables- page 41	Tuna salad with pears- page 36 Red Beans & Rice- page 37	Southwest based potatoes- page 44
Homework:	3 day food log	Try one new recipe from cookbook	Try one new recipe from cookbook	Try one new recipe from cookbook	

CaRDS RCT – CONSORT Flow Diagram
